10.9 Intensity of Attack Scale

The Intensity of Attack scale is designed to assess the severity of the last vomiting/retching episode at the time of assessment. Severity ranges from Mild to Excruciating on a 4 point scale. This scale will be adapted for the ePD and patients will be prompted to answer the questions according to the Schedule of Events (Table 1).

10.10 Prior Episode Questionnaire

The Prior Episode Questionnaire is designed to compare the overall intensity and duration of the current CVS episode with CVS episodes that the patient has typically experienced in the past. For both Intensity and Duration, the patient will respond whether the current episode overall was Less than, the Same as, or Greater than their typical previous CVS episodes. The questions will be prompted approximately 24 hours after each dose of study medication is administered.

11 ADVERSE EVENTS

11.1 Definition of Adverse Events

An adverse event is any untoward medical occurrence that may appear or worsen in a patient during the course of a study. It may be a new intercurrent illness, a worsening concomitant illness, an injury, or any concomitant impairment of the patient's health, including laboratory test values, regardless of etiology. Any worsening (i.e., any clinically significant adverse change in the frequency or intensity of a pre-existing condition) should be considered an adverse event. A diagnosis or syndrome should be recorded on the adverse event page of the eCRF rather than the individual signs or symptoms of the diagnosis or syndrome.

All patients will be monitored for adverse events during the study. Assessments may include monitoring of the following parameters: the patient's clinical symptoms, laboratory, physical examination findings, or findings from other tests and/or procedures.

An adverse event reported after informed consent, but before the first dose of study medication, will be considered a pretreatment adverse event (or interim medical event) and will be captured on the eCRF. Adverse events will be considered treatment-emergent if the onset is after the first dose of study drug.

An abnormal laboratory value is considered to be an adverse event if the abnormality:

- Is considered clinically significant; OR
- results in discontinuation from the study; OR
- is judged by the Investigator to be of significant clinical importance requiring treatment, modification/interruption of investigational product dose, or any other therapeutic intervention.

Regardless of severity grade, only laboratory abnormalities that fulfill a seriousness criterion need to be documented as a serious adverse event.

If a laboratory abnormality is one component of a diagnosis or syndrome, then only the diagnosis or syndrome should be recorded on the adverse event eCRF. If the abnormality was not a part of a diagnosis or syndrome, then the laboratory abnormality should be recorded as the adverse event. If possible, the laboratory abnormality should be recorded as a medical term and not simply as an abnormal laboratory result (e.g., record thrombocytopenia rather than decreased platelets).

11.2 Evaluation of Adverse Events

A qualified Investigator will evaluate all adverse events as to seriousness, severity/intensity, and relationship to Study Medication, duration, action taken, and outcome.

11.2.1 Serious Adverse Event (SAE)

A serious adverse event is an adverse event, as per Title 21 CFR 312.32 and ICH E2A.II.B that fulfills the following criteria:

- Is fatal (results in death);
- Is life-threatening (Note: the term "life-threatening" refers to an event in which the patient was at risk of death at the time of the event; it does not refer to an event that could hypothetically have caused death had it been more severe);
- Requires inpatient hospitalization or prolongation of existing hospitalization (hospitalization is defined as an inpatient admission, regardless of length of stay);
- Results in persistent or significant disability/incapacity (a substantial disruption of the patient's ability to conduct normal life functions);
- Is a congenital anomaly/birth defect; or
- Constitutes an important medical event that may jeopardize the patient or may require medical or surgical intervention to prevent one of the other outcomes listed above.

Important medical events are defined as those occurrences that may not be immediately life-threatening or result in death, hospitalization, or disability, but may jeopardize the patient or require medical or surgical intervention to prevent one of the other outcomes listed above. Examples of such medical events include allergic bronchospasm requiring intensive treatment in an emergency room or at home, blood dyscrasias or convulsions that do not result in inpatient hospitalization.

Events **not considered** to be serious adverse events are hospitalizations for:

- A procedure for protocol/disease-related investigations (e.g., sampling for laboratory tests). However, hospitalization or prolonged hospitalization for a complication of such procedures remains a reportable serious adverse event.
- Hospitalization or prolongation of hospitalization for technical, practical, or social reasons, in absence of an adverse event.
- A procedure that is planned (i.e., planned prior to the starting of treatment on study); must be documented in the source document and the eCRF. Hospitalization or prolonged hospitalization for a complication remains a reportable serious adverse event.
- An elective treatment of or an elective procedure for a pre-existing medical condition that does not worsen.
- Emergency outpatient treatment or observation that does not result in admission, unless fulfilling other seriousness criteria above.
If an adverse event is considered serious, the adverse event eCRF must be completed.

For each serious adverse event, the Investigator will provide information on severity, start and stop dates, relationship to investigational product, action taken regarding investigational product, and outcome.

Queries pertaining to serious adverse events will be handled through the electronic data capture system or other appropriate means. Urgent queries (e.g., missing causality assessment) may be handled by telephone.

11.2.2 Severity/Intensity

For both adverse events and serious adverse events, the Investigator must assess the severity/intensity of the event.

The National Cancer Institute-Common Terminology Criteria for Adverse Events (CTCAE) Version 5.0 should be used to grade the severity/intensity of all events. These criteria will be provided in a study manual. If a CTCAE criterion does not exist, the Investigator should grade the severity according to the following criteria:

- Grade 1 (mild): does not interfere with the patient's usual function
- Grade 2 (moderate): interferes to some extent with patient's usual function
- Grade 3 (severe): interferes significantly with patient's usual function
- Grade 4 (life-threatening): results in a threat to life or in an incapacitating disability
- Grade 5 (death): results in death

The term "severe" is often used to describe the intensity of a specific event (as in mild, moderate or severe myocardial infarction); the event itself, however, may be of relatively minor medical significance (such as severe headache). This criterion is not the same as "serious" which is based on patient/event outcome or action criteria associated with events that pose a threat to a patient's life or functioning.

Seriousness, not severity, serves as a guide for defining regulatory obligations.

11.2.3 Relationship to Study Medication

Relationship should be assessed and provided for every adverse event/serious adverse event based on currently available information. Relationship is to be reassessed and provided as additional information becomes available. Adverse events will be classified by the Investigator as follows:

Related for Regulatory Reporting Assessment:

Definitely Related: There is clear evidence to suggest a causal relationship, and other possible contributing factors can be ruled out. The clinical event, including an abnormal laboratory test result, occurs in a plausible time relationship to drug administration and cannot be explained by concurrent disease or other drugs or chemicals. The event resolves or improves upon withdrawal of drug (de-challenge). The event would be considered as definitely related to the Study Medication upon results of a positive re-challenge procedure.

Probably Related: There is evidence to suggest a causal relationship (e.g., the event occurred within a reasonable time after administration of the trial medication). However, the influence of other factors that may have contributed to the event (e.g., the patient's clinical condition, other concurrent disease, concomitant medications or events) is unlikely, and the event follows a clinically reasonable response upon withdrawal of drug (de-challenge).

Possibly Related: There is evidence to suggest a causal relationship (e.g., the event occurred within a reasonable time after administration of the Study Medication). However, the influence of other factors may have contributed to the event (e.g., the patient's clinical condition, other concurrent disease, concomitant medications or events).

Unrelated for Regulatory Reporting Assessment:

Unlikely Related: A clinical event, including an abnormal laboratory test result, whose temporal relationship to drug administration makes a causal relationship improbable (e.g., the event did not occur within a reasonable time after administration of the trial medication) and in which other drugs or concurrent or underlying disease provide plausible explanations (e.g., the patient's clinical condition, other concomitant treatments).

Not related: The adverse event is completely independent of Study Medication administration, and/or evidence exists that the event is definitely related to another etiology. There must be an alternative, definitive etiology documented by the clinician.

11.2.4 Duration

For all adverse events whether or not considered serious, the Investigator will provide a record of the start and stop dates of the event. Every effort should be made to resolve all adverse events with continued follow-up with the patient until appropriate resolution can be achieved. If an event is unresolved at the end of the study it will be recorded as ongoing.

11.2.5 Action Taken

The Investigator will record the action taken with investigational product as a result of an adverse event or serious adverse event on the eCRF, as applicable (e.g., discontinuation, or interruption of investigational product, as appropriate) and record if concomitant and/or additional treatments were given for the event.

11.2.6 Outcome

The Investigator will record the outcome of adverse events on the eCRF, as applicable (e.g., recovered, recovered with sequelae, not recovered, or death (due to the adverse event)).

11.3 Follow-Up

Adverse events assessed as not related to Study Medication, including clinically significant laboratory tests, ECGs, or physical examination findings, must be followed until the event resolves, the condition stabilizes, the event is otherwise explained, or the final study visit occurs, whichever comes first.

Adverse events assessed as related to Study Medication and serious adverse events will be followed for as long as necessary to adequately evaluate the patient's safety, or until the event stabilizes, is otherwise explained, death occurs, or the patient is lost to follow-up. If resolved, a resolution date should be provided. The Investigator is responsible for ensuring that follow-up includes any supplemental investigations indicated to elucidate the nature and/or causality of the adverse event. This may include additional clinical laboratory testing or investigations, examinations, or consultation with other health care professionals as is practical.

11.4 Pregnancy

The Sponsor must be informed within 24 hours upon learning that a patient, or male patient's partner, has become pregnant any time after the first dose of Study Medication until 4 weeks after the last dose of Study Medication. Patient pregnancies (or pregnancy of a male patient's partner) must be followed until termination of pregnancy or the birth of the child.

If a female partner of a male patient taking investigational product becomes pregnant, the male patient taking the investigational product should notify the Investigator, and the pregnant female partner should be advised to call her healthcare provider immediately.

11.5 Recording Adverse Events

All adverse events (regardless of seriousness or relationship to Study Medication) including those from the time informed consent is obtained through to the final study visit are to be recorded in the eCRF. Each individual adverse event is to be listed as a separate entry. The Investigator will provide information about dates of onset and resolution, seriousness, severity, action(s) taken, outcome, and relationship to the Study Medication. All adverse events should be documented in the patient's source documents.

11.6 Reporting Adverse Events

The Investigator must report to Sponsor or its designee all adverse events that occur during the study from the time written informed consent is given until the final study visit or early termination, regardless of their relationship to the Study Medication. Serious adverse events and pregnancies will be reported from the time written informed consent is given through 30 days beyond the last dose of Study Medication.

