Randomized participants without clinical observations in the 2-hour observation period will be asked to treat a subsequent CVS episode (with single daily dosing up to 5 consecutive days) within 12 weeks after the randomization date. Enrolled participants will self-administer the study medication when they know their CVS episode is imminent or as soon as possible after a CVS-related vomiting episode has begun. Participants will interact with their ePD prior to initiation of treatment (if possible) and to capture the study data. The ePD will be used to record the date and time of study medication administration, the number of vomiting and retching events, and the participant reported outcome measures (including the intensity and duration of the CVS episode, severity of abdominal pain, nausea, and anxiety/panic, and characteristics of the nausea, vomiting and retching over defined time periods) (section 5.8). Participants will also record the number of vomiting and retching events in the 24 hours after dosing on a paper questionnaire.

Participants will be instructed to contact the Research Clinic at the earliest possible time after initiation of dosing and at any time should they require rescue medication, medical assistance or experience an intolerable AE at home during the treatment period. Participants will record rescue medications taken after administration of study medication in their ePD and on a paper concomitant medications form. Rescue medication may include any agent(s) from the list described in Section 9.8 of the protocol. Participants are encouraged to avoid rescue medication for the first 2 hrs. following treatment with the study medication.

Participants will be required to return to the Research Clinic (Visit 3) within 3-5 days from the last study medication administration for final in-clinic assessments, to return the Patient Kit containing the used and unused study medication, ePD, and any other unused supplies. Conversely, participants will be asked to return to the Research Clinic after 12 weeks with their unused Patient Kit if they did not treat a CVS episode within this time period.

Visit 3 will include the following assessments: Vital signs; full physical examination; assessment for treatment emergent adverse events; 12- lead ECG, concomitant medications (including rescue medication taken), and clinical labs.

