9.1 ADVERSE EVENTS

An adverse event reported after informed consent, but before the first dose of study medication, will be considered a pre-treatment adverse event (or interim medical event). Treatment-emergent adverse events (TEAEs) will be defined as any adverse event that occurs after administration of the first dose of study medication until the Follow Up Visit or the Early Termination Visit. The number and percentage of participants who report TEAEs will be summarized by system organ class and preferred term.

Treatment emergent adverse events will also be summarized by intensity as well as relationship to study drug.

Participants who report the same preferred term on multiple occasions will be counted once for the preferred term: under the highest severity when summarized by severity and under the closest relationship to study medication when summarized by relationship. If a participant reports multiple preferred terms for a system organ class, the participant will be counted only once for that system organ class.

The number and percentage of participants who experience TEAEs will be summarized by dosing regimen for the following:

- By system organ class and preferred term
- By severity/intensity, system organ class, and preferred term
- By relationship to study drug, system organ class, and preferred term
- Serious adverse events by system organ class and preferred term

- Serious adverse events by relationship to study drug, system organ class, and preferred term
- Adverse events resulting in discontinuation of study medication by system organ class and preferred term
- Adverse events that result in study medication dose interruption by system organ class and preferred term

Clinically significant deteriorations in physical examination findings (in the opinion of the investigator) are captured and summarized as adverse events.

By-participant listings will be provided for any deaths, serious adverse events, and adverse events leading to discontinuation of treatment.

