11.6.1 Reporting Serious Adverse Events

The Investigator is required to notify the Sponsor, and the Sponsor's designated Drug Safety Unit within 24 hours after becoming aware of the occurrence of a serious adverse event. All serious adverse events will be reported through completion of the adverse event eCRF. The Investigator will be responsible for reporting serious adverse events to the IRB.

Medical Monitor and Emergency Contact Information:

[name], Medical Director, Cognitive Research Corporation [name] [contact] [contact] e-mail: [contact]

If an Investigator becomes aware of a serious adverse event within 30 days after the last dose of Study Medication and it is considered by him/her to be caused by the Study Medication with a reasonable possibility, the event must be documented and reported through completion of the adverse event eCRF.

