12.6.3 Safety

All safety summaries will be descriptive with no statistical hypothesis testing and based on the Safety Population. All safety endpoints will be listed in by-patient data listings.

Adverse events will be coded using MedDRA and summarized by system organ class and preferred term. Clinically significant deteriorations in physical examination findings will be reported and summarized as adverse events.

Laboratory values will be converted to the project-defined unit of measurement, as applicable, before analysis. Abnormal, clinically significant laboratory values will be reported and summarized as adverse events.

Adverse Events

An adverse event reported after informed consent, but before the first dose of study medication, will be considered a pre-treatment adverse event (or interim medical event). Treatment-emergent adverse events (TEAEs) will be defined as any adverse event that occurs after administration of the first dose of study medication until the Follow Up Visit or the Early Termination Visit. The number and percentage of patients who report TEAEs will be summarized by system organ class and preferred term.

Treatment emergent adverse events will also be summarized by intensity as well as relationship to study drug.

Patients who report the same preferred term on multiple occasions will be counted once for the preferred term: under the highest severity when summarized by severity and under the closest relationship to study medication when summarized by relationship. If a patient reports multiple preferred terms for a system organ class, the patient will be counted only once for that system organ class.

The number and percentage of patients who experience TEAEs will be summarized by dosing regimen for the following:

- By system organ class and preferred term
- By severity/intensity, system organ class, and preferred term
- By relationship to study drug, system organ class, and preferred term
- Serious adverse events by system organ class and preferred term
- Serious adverse events by relationship to study drug, system organ class, and preferred term

- Adverse events resulting in discontinuation of study medication by system organ class and preferred term
- Adverse events that result in study medication dose interruption by system organ class and preferred term

By-patient listings will be provided for any deaths, serious adverse events, and adverse events leading to discontinuation of treatment.

Clinical Laboratory

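### For home-treated participants, SAEs are collected to 30 days after the last dose but tabulated only to Visit 3, 3 to 5 days after it

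*Combined protocol and SAP*

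**What the plan says.** **Collection.** Protocol 11.6 says that SAEs and pregnancies "will be reported from the time written informed consent is given through 30 days beyond the last dose of Study Medication". It attaches no causality condition. Protocol 11.6.1 repeats the 30 days more narrowly: an investigator who "becomes aware of a serious adverse event within 30 days after the last dose of Study Medication" must document it if it is also considered to be caused by study medication. Protocol 11.5 sends adverse events of any seriousness to the eCRF up to the final study visit.

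**Treatment-emergent window.** SAP 9.1 defines a treatment-emergent adverse event (TEAE) as "any adverse event that occurs after administration of the first dose of study medication until the Follow Up Visit or the Early Termination Visit". Protocol 12.6.3 has the same end point, "until the Follow Up Visit or the Early Termination Visit". Protocol 11.1 gives a start and no end: "Adverse events will be considered treatment-emergent if the onset is after the first dose of study drug".

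**Tables.** In SAP 9.1 the planned summaries follow one lead-in: "The number and percentage of participants who experience TEAEs will be summarized by dosing regimen for the following". Two of the summaries under it concern SAEs: "Serious adverse events by system organ class and preferred term", and the same split by relationship to study drug. Protocol 12.6.3 has the same structure. No other SAE table is planned. By-participant listings of deaths and SAEs are also planned, and they are not limited to TEAEs.

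**Timing of Visit 3.** SAP 5.3 has participants who treat an episode return "within 3-5 days from the last study medication administration". Those who treat no episode return after 12 weeks.

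**The concern.** The collection window and the tabulation window end at different times. An SAE with onset after Visit 3 but within 30 days of the last dose is inside the period that protocol 11.6 sets for collection and outside the period that the SAE tables count.

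Safety is one of the two primary objectives, and SAP 9 makes all safety summaries descriptive. The arm-level counts and percentages are therefore the comparative safety result, with no further analysis behind them. With about 50 participants per arm, one uncounted participant with an SAE moves that arm's rate by about 1/50 = 2 percentage points. The late events that 11.6.1 singles out, those judged caused by study medication, are also the ones that the SAE-by-relationship table would miss.

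**Working it through.** The plan states no figure on this point, so there is none to reproduce. The check is interval arithmetic.

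**Inputs**
- End of SAE collection: 30 days after the last dose (protocol 11.6).
- End of the TEAE window: Visit 3 or early termination (SAP 9.1, protocol 12.6.3).
- *v*, days from last dose to Visit 3 in participants who treat at home: 3 to 5 (SAP 5.3).
- Visit 3 in participants who never treat: after 12 weeks, about 12 × 7 = 84 days after their only dose, the in-clinic dose at Visit 2.
- *L*, days from the Visit 2 dose to the last home dose: not given for any participant. Values from 1 to 84 are assumed below to show the range.
- *s*, screening days before Visit 2: up to 14.

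**Step 1. Post-last-dose segment, home-treated participants.** Untabulated days = 30 − *v*.
- *v* = 5: 30 − 5 = 25 days; 25/30 = 83%.
- *v* = 3: 30 − 3 = 27 days; 27/30 = 90%.

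**Step 2. The same days as a share of longer windows.** From first dose the share is (30 − *v*)/(*L* + 30). From consent it is (30 − *v*)/(*s* + *L* + 30), here with *s* = 14.

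| *L* (assumed) | From first dose | From consent, *s* = 14 |
|---|---|---|
| 1 | 25/31 to 27/31 = 81% to 87% | 25/45 to 27/45 = 56% to 60% |
| 14 | 25/44 to 27/44 = 57% to 61% | 25/58 to 27/58 = 43% to 47% |
| 28 | 25/58 to 27/58 = 43% to 47% | 25/72 to 27/72 = 35% to 38% |
| 84 | 25/114 to 27/114 = 22% to 24% | 25/128 to 27/128 = 20% to 21% |

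From first dose, the share exceeds one half only if *L* < 2(30 − *v*) − 30, that is, below 20 days (*v* = 5) or 24 days (*v* = 3).

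**Step 3. Participants who never treat.** Visit 3 at about day 84 is later than day 30, so the gap is 0 days.

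**Step 4. Early termination.** Protocol 8.3.1 has Visit 3 assessments performed as an Early Termination Visit but gives no interval from the last dose. A participant stopped after the in-clinic dose may have a similar gap, but the documents do not allow it to be sized.

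**Step 5. What reaches the database after Visit 3.** Under 11.6, every SAE to day 30. Under the last paragraph of 11.6.1, only those considered caused by study medication. The gap in the tables exists on either reading, but the number of events that could fall into it differs.

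**The case against.** The strongest defence is that ending treatment-emergence at Visit 3 is a reasonable exposure-based choice. Protocol 7.4 gives a half-life of 10 hours, so 3 to 5 days is 72/10 to 120/10, or about 7 to 12 half-lives. The end point is the same in SAP 9.1 and protocol 12.6.3, and a reporting window longer than the tabulation window is not in itself an error. This stands as a reason to expect few drug-related SAEs after Visit 3. It does not explain why events that the protocol chose to collect for 30 days should enter no arm-level count.

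A second point also stands. The Schedule of Events has no contact after Visit 3, so later SAEs depend on the investigator becoming aware of them, and 11.6.1 may restrict them to related events. Pooling them without distinction with events found by active follow-up would mix two kinds of ascertainment. This bears on how late events are shown, and the fix allows for it.

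Three stronger readings are tempting and are not supported:
- *Most of the SAE surveillance window is left out.* The window in 11.6 starts at consent. Over that window the untabulated share depends on when the episode is treated, and it is a minority for late treaters.
- *Late SAEs would go unreported.* The SAE and death listings carry no TEAE restriction, so late events are uncounted, not hidden. One loose end is that SAP 6.1 provides listings up to study completion or withdrawal, so it is worth confirming that post-Visit 3 events are included.
- *Protocol 11.1 contradicts 12.6.3.* It leaves the end of the window open, and the other two sections supply one. The SAP also states that it supersedes the protocol's statistical text. The definition is incomplete, not opposed.

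**Conclusion.** The point holds for participants who treat an episode at home. SAEs with onset in 25 to 27 of the 30 days after the last dose, 83% to 90% of that segment, would be in neither SAE table and in no arm-level percentage. Participants who never treat are unaffected.

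The conclusion rests on reading the TEAE lead-in as governing the SAE summaries beneath it, which is the natural reading, and on Visit 3 taking place on schedule. The percentages are shares of days, not of events. The documents give no SAE rate, so the number of events affected cannot be estimated and may be small or nil. It would be too much to say that the reported rates will understate SAEs; they will do so only if such an event occurs. The change is worth making because safety is a primary objective and the correction is cheap.

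**What to change.** 1. In SAP 9.1 and protocol 12.6.3, state that SAE and death summaries include events with onset from first dose through the later of Visit 3 or 30 days after the last dose. Show post-Visit 3 SAEs as a separate row or table, with a note that their ascertainment is passive.
2. Keep the Visit 3 cut-off for non-serious adverse events, whose collection ends there.
3. Add the matching end of window to protocol 11.1.
4. Reconcile protocol 11.6 (all SAEs to 30 days) with 11.6.1 (only those considered caused by study medication), so that the content of the 30-day count is defined.

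**Cost.** In the SAP, one rule and one programming flag. No new data are needed if 11.6 was followed. If sites applied the narrower wording of 11.6.1, unrelated late SAEs may not be in the database, and the late row must be labelled accordingly. Protocol 13.4 treats any change to the protocol as an amendment, so items 3 and 4 and the protocol part of item 1 carry that burden. SAE percentages may be slightly higher, and the late counts will rest on passive reporting.
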